## 13 Adverse events

## 13.1 Definition and classification of adverse events

Adverse events (AEs) and serious adverse events (SAEs) are defined in Appendix 1.

Classification of AEs in terms of severity, causality, and outcome is defined in Appendix 2.

# 13.2 Collection of adverse event reports

AE data must be collected from time of first trial-related activity after the subject has signed the informed consent form (ICF) until subject's completion of the clinical trial (safety follow-up visit at week 32 see Section 7.3)

AEs must be assessed by a physician.

At all visits, the subject will be asked a non-leading question by the investigator about AEs, e.g.: "How have you felt since I saw you last?" No specific symptoms should be asked for. It is important that the investigator also observes the subject for any changes not reported by the subject and records these changes.

Principles for data entry in the eCRF are described in Sections 11.4.1 to 11.4.5

# 13.3 Reporting of adverse events

AEs reported by the subject or observed by the investigator must be recorded on the AE form of the eCRF and should be described in the following manner:

The *AE term* must be in precise English medical terminology (that is, not necessarily the exact words used by the subject). Whenever possible, a specific diagnosis should be stated (e.g., 'allergic contact dermatitis').

The *duration* of the AE must be reported by the start date and stop date of the event, unless the event is ongoing. If the event is ongoing, it will be marked as ongoing. In addition, it will be recorded if the AE started prior to first administration of IMP.

AEs must be classified in terms of severity, causality, and outcome according to the definitions in Appendix 2.

Action taken with IMP: any action taken with IMP as a consequence of the AE must be recorded (dose not changed, drug interrupted, drug withdrawn, not applicable, unknown).

Page 89 of 129

Version: 5.0

Other action taken: any other action taken as a result of the AE must be recorded (none, concomitant medication, concurrent procedure).

It must be recorded in the eCRF if the AE led to permanent discontinuation of IMP and/or withdrawal from trial.

Withdrawn from trial due to this AE: it must be recorded whether the AE led to withdrawal from the trial.

# 13.4 Reporting of serious adverse events

The criteria that define an AE as serious (that is, an SAE) are defined in Appendix 1. SAE criteria are also listed on the SAE form.

# 13.4.1 Investigator reporting responsibilities

Any SAE must be reported to LEO Pharma on the (paper) SAE form immediately, without undue delay and no later than 24 hours of obtaining knowledge. This report should contain amongst others an assessment of available information on seriousness, severity, causal relationship to the IMP, comparator or trial procedure, the action taken, the outcome to date, and a narrative description of the course of the event. For more details regarding reporting of any SAE, please see the guidance text on the SAE form.

By signing and dating the SAE form, the investigator acknowledges that he/she is aware of the SAE and has assessed the causal relationship of the IMP(s) and any of the other medications to the SAE.

The actual reporter, if not the investigator, should also sign and date the SAE form.

The completed SAE form must be faxed or scanned and e-mailed to Global Safety at LEO Pharma using the e-mail address or fax number below:

#### Global Safety at LEO Pharma

E-mail address: [contact]

[contact]

If relevant, the investigator will enclose other information with the SAE form, such as anonymised reports of diagnostic procedures, hospital records, autopsy reports, etc.

Additionally, Global Safety at LEO Pharma may request further information in order to fully assess the SAE. The investigator must forward such information to LEO Pharma upon request by fax or e-mail (see contact details above).

The investigator must notify the local IRB(s)/IEC(s) of SAEs, as required by current applicable legislation for the concerned country.

SAEs occurring after the completion of the clinical trial, including any protocol-required post-treatment follow-up period, should not be routinely sought or recorded. However, such events should be reported immediately without undue delay and no later than 24 hours of obtaining knowledge to Global Safety at LEO Pharma (see contact details above) if the investigator becomes aware of them.

## 13.4.2 LEO Pharma reporting responsibilities

Global Safety at LEO Pharma is responsible for assessing whether an SAE is expected. The relevant reference safety information documents for this clinical trial are:

- For the drug product LEO 138559, the investigator's brochure Section 7.3.8, edition 4 and subsequent updates must be used.
- For the comparator Dupixent® the latest version of the SmPC [54] must be used.

Global Safety at LEO Pharma will notify the regulatory authorities and concerned investigators of SAEs according to the current applicable legislation for the concerned country.

The IRB(s)/IEC(s) will be notified of SAEs according to the current applicable legislation for the concerned country.

For all non-US countries, the following reporting requirements apply: all SAEs which are assessed as causally related to the IMP(s) by either the investigator or LEO Pharma [55], and which are unexpected (suspected, unexpected serious adverse reactions [SUSARs]), are subject to expedited reporting to regulatory authorities and IEC(s)/IRB(s) according to the current applicable legislation in the concerned countries. Investigators will be notified of the evolving safety profile of the IMP on an ongoing basis.

# 13.5 Other events that require expedited reporting

# 13.5.1 Pregnancy

Any pregnancy, occurring after first exposure to IMP and until the subject has completed the trial must be reported to LEO Pharma within 24 hours of first knowledge using the (paper)

pregnancy form (part I). All pregnancies must be followed up until delivery or termination, and outcome must be reported on the (paper) pregnancy form (part II) within 24 hours of first knowledge.

The completed pregnancy forms must be faxed or scanned and e-mailed to Global Safety at LEO Pharma. Contact details are given in Section 13.4.1.

Pregnant subjects must immediately discontinue IMP permanently (Sections 10.2.1 and 10.3).

# 13.6 Reporting of other events

#### 13.6.1 Medication error

Medication error refers to any unintentional error in the dispensing or administration of an IMP.

Medication errors include accidental overdose or underdose, inappropriate schedule of product administration, incorrect route of product administration, wrong product administered, and expired product administered.

Accidental overdose or underdose where a clinical consequence occurred or could have occurred should be recorded based on investigator judgement.

Inappropriate schedule of product administration where a clinical consequence occurred or could have occurred should be recorded based on investigator judgement. Treatment non-compliance (incl. missed doses) where no clinical consequence occurred or could have occurred should not be recorded as medication errors. See Section 9.8.4 for recording of treatment compliance.

## Reporting in eCRF

Medication error must be recorded on the AE from in the eCRF. In addition, any clinical consequences of the medication error must be recorded as separate AEs on the AE form. If the AE originating from the medication error qualifies as an SAE, expedited reporting is required (Section 13.4).

#### 13.6.2 Misuse or abuse

The terms misuse and abuse are similar in that they both represent the intentional use of a drug in a way other than intended.

Misuse refers to situations where the IMP is intentionally and inappropriately used for therapeutic purposes not in accordance with the protocol.

Abuse refers to intentional use of an IMP for what could be considered desirable non-therapeutic effects (e.g. sedative, stimulant, euphoric effects).

Misuse and abuse must be recorded on the AE form in the eCRF. In addition, any clinical consequences of misuse or abuse must be recorded as separate AEs on the AE form. If the AE originating from the misuse or abuse qualifies as an SAE, expedited reporting is required (Section 13.4).]

#### 13.6.3 Aggravation of condition

Any clinically significant aggravation/exacerbation/worsening of any medical condition(s) (including the trial disease), compared to screening, must be reported as an (S)AE in accordance with Sections 13.3 and 13.4.

Atopic dermatitis is a fluctuating disease with possible periods of remission. In case of relapses/recurrences, only aggravations/exacerbations exceeding normal disease fluctuation or lesions appearing in a body area normally not affected by AD should be reported as an AE.

# 13.7 Follow-up for final outcome of adverse events

During the trial, the investigator should follow up for final outcome on all AEs (including SAEs). Once a subject leaves the clinical trial, the investigator should follow up on the outcome of all non-serious AEs classified as possibly or probably related to the IMP for 2 weeks after visit 16 or until the final outcome is determined, whichever comes first. Non-serious AEs classified as not related to the IMP do not need to be followed up for the final outcome.

All SAEs must be followed up until a final outcome has been established, that is, the follow-up may continue beyond the end of the clinical trial. For SAEs which have stabilised and from which the subject cannot be expected to recover during the trial or the safety follow-up periods, e.g. chronic or stabilised conditions, the final outcome at the investigator's discretion should be reported as 'recovering/resolving' or 'not recovered/not resolved'. In addition, a statement detailing why the subject cannot be expected to recover during the trial, e.g. that the SAE has stabilised or is chronic, should be added to the narrative description of the SAE on the SAE form.

## 13.8 Handling of an urgent safety measure

An urgent safety measure is a measure taken to implement an action/protocol deviation under an emergency. This is defined as "...the occurrence of any new event relating to the conduct of the trial or the development of the investigational medicinal product where that new event

Trial ID: LP0145-2274 Date: **04-Jan-2023** Version: 5.0 Page 93 of 129

is likely to affect the safety of the subjects, the sponsor and the investigator shall take appropriate urgent safety measures to protect the subjects against any immediate hazard." [56].

If the investigator becomes aware of information that requires an immediate change in a clinical trial procedure or a temporary halt of the clinical trial to protect clinical trial subjects from any immediate hazard to their health and safety, the investigator can do so without prior approval from LEO Pharma, regulatory authorities, or IRBs/IECs.

The investigator must immediately inform LEO Pharma – by contacting the clinical project manager or medical expert – of this change in a clinical trial procedure or of the temporary halt; the investigator will provide full details of the information and the decision-making process leading to the implementation of the urgent safety measure.

LEO Pharma must act immediately upon receipt of the urgent safety measure notification in accordance with internal procedures and local legislation.

## 14 Statistical methods

# 14.1 Sample size

The sample size of 12 subjects evaluable for the primary endpoint i.e., for whom a lesional biopsy is available at baseline and week 4 (8 receiving LEO 138559 and 4 receiving comparator) is based on the trial design for the exploratory comparison of the molecular signature changes of LEO 138559 and the comparator. The sample size is not based on power calculations.

# 14.2 Trial analysis sets

All screened subjects will be accounted for in the CTR.

All subjects randomised and exposed to IMP will be included in the full analysis set and will be analysed for efficacy based on the planned (randomized) treatment allocation. Exclusions from the full analysis set can be considered in special cases as described in ICH E9, Section 5.2.1., Full Analysis Set. If it is decided to exclude a randomised subject from the full analysis set, a justification addressing ICH E9 will be given.

A safety analysis set will be defined as all subjects who received IMP and will be analyzed according to the actual treatment received.

A PK analysis set will be defined as all subjects who were exposed to LEO 138559 and provided at least one sample for measuring serum concentrations of LEO 138559.

The decisions regarding inclusion/exclusion of subjects or subject data from the trial analysis sets will be documented in the clinical trial report.

# 14.3 Statistical analysis

## 14.3.1 Disposition of subjects

The reasons for permanent discontinuation of IMP or withdrawal from trial will be presented for all randomised subjects by last visit attended and by treatment group and overall.

A subject disposition summary table will be made including information of number of subjects who were screened, randomised, exposed and who completed the trial, permanently discontinued IMP, and/or were withdrawn from the trial (by treatment group and overall)

#### 14.3.2 Demographics and other baseline characteristics

Descriptive statistics of demographics and other baseline characteristics will be presented for all randomised subjects and by treatment group and overall. Presentations of age, sex,

ethnicity, race, and baseline EASI score by treatment group will be reported for all randomised subjects. Other baseline characteristics include height, weight, BMI, duration of AD, concurrent diagnoses (from medical history and indications for concomitant medication), concomitant medication, and previous AD treatments.

#### 14.3.3 Exposure and treatment compliance

Exposure to treatment will be presented for the safety analysis set as days of exposure per treatment group and overall.

The cumulated dose administered to each subject will be determined and summarised descriptively. For subjects who withdraw from the trial, are lost to follow-up, or permanently discontinue IMP, their cumulated dose will be calculated up until the time of withdrawal/permanent discontinuation of IMP/loss to follow-up.

Treatment compliance will be presented for the safety analysis set per treatment group as the percentages of missed IMP doses. In addition, the percentage of subjects who received IMP application according to dosing schedule will be presented per treatment group.

## 14.3.4 Testing strategy

No formal statistical significance tests will be carried out.

## 14.3.5 Primary endpoint analysis

The primary endpoint

 Change in biomarkers in lesional skin biopsies typically associated with atopic dermatitis from baseline to week 4

will be analyzed descriptively by computing the following statistics by treatment group: minimum and maximum value, lower and upper quartile, median, mean, standard deviation and median absolute deviation.

Individual and mean data as well as boxplots will be plotted by treatment group.

## 14.3.6 Secondary endpoint analysis

The secondary endpoint

• Number of treatment-emergent adverse events from baseline to week 16 per subject

will be analysed descriptively on the safety analysis set by computing the number of treatment-emergent adverse events per subject by treatment group.

Trial ID: LP0145-2274 Date: **04-Jan-2023** Version: 5.0 Page 96 of 129

An event will be considered treatment-emergent if started after the first dose of IMP or if started before the first dose of IMP and worsened in severity after first dose of IMP. An event will not be considered treatment-emergent if starting 18 weeks after the last dose of IMP.

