# 4 Schedule of trial procedures

**Panel 2: Schedule of trial procedures** 

							Treat	tment								l l	
	Screening a)	Washout phone call a)	Baseline/ Start of treatment			Primary endpoint visit b)						End of treatment c)	SFU phone calls	SFU site visit End of trial visit c)	Early termination e)	Unscheduled. visit 	References (protocol section)
Visit	1	2 a)	3	4	5	6	7	8	9	10	11	12	13, 14, 15	16			
Week	-4	-1	0	1	2	4	6	8	10	12	14	16	20, 24, 28	32			
Day	Up to - 28	-7	1	8	15	29	43	57	71	85	99	113	141, 169, 197	225			
Visit window (days)	NA	NA	NA	±1	±3	±3	±3	±3	±3	±3	±3	±3	±3	±3			
Trial population and	eligibili	ty															
Informed consent g)	X																Appendix 3B: Informed consent process
Subjects' eligibility	X		X														8.2 and 8.3
Investigator assessme	ents at so	creenin	g and/o	r base	eline o	only											
Demographics	X																11.2.1
Body assessment (height)	X																11.2.3

THIS DOCUMENT CONTAINS CONFIDENTIAL INFORMATION AND MUST NOT BE COPIED OR MADE AVAILABLE TO ANY THIRD PARTY WITHOUT THE PRIOR WRITTEN CONSENT OF THE LEO PHARMA GROUP

Page 25 of 129

							Treat	tment							(e)	G	_
	Screening a)	Washout phone call a)	Baseline/ Start of treatment			Primary endpoint visit b)						End of treatment ©	SFU phone calls	SFU site visit End of trial visit e)	Early termination e)	Unscheduled. visit f)	References (protocol section)
Visit	1	2 a)	3	4	5	6	7	8	9	10	11	12	13, 14, 15	16			
Week	-4	-1	0	1	2	4	6	8	10	12	14	16	20, 24, 28	32			
Day	Up to - 28	-7	1	8	15	29	43	57	71	85	99	113	141, 169, 197	225			
Visit window (days)	NA	NA	NA	±1	±3	±3	±3	±3	±3	±3	±3	±3	±3	±3			
Medical history	X		(X)h)														11.2.2
Hepatitis B, C, HIV	X																11.4.5
Tuberculosis (Mycobacterium tuberculosis IFN-γ release assay) i)	X																11.4.5
Serum pregnancy test (females only) j)	X																11.4.5
Randomisation and t	treatmen	its															
Randomisation k)			X														9.3.1
IMP administration at the trial site k)			X	X	X	X	X	X	X	X	X					(X)	9.2

			t t				Treat	tment							 	G.	

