### **Treatment period (week 1 to week 16)**

After confirmation of the eligibility at the visit 3 (day 1) the assessments as specified in Panel 2 and Panel 6 (sequence of assessments) will be performed and the subjects will be randomised. LEO 138559 or comparator injections will be administered at the trial site by site staff Q2W for 16 weeks (Section Administration of investigational medicinal products 9.2). Only site staff responsible for handling of IMPs and preparation and administration of the injections will be unblinded and will not be involved in the efficacy and safety assessments during the trial. In addition to the Q2W dosing schedule, the LEO 138559 treatment group will receive an additional dose of their allocated treatment at visit 4 (week 1). Subjects randomised in the comparator treatment group will receive the same number of injections as subjects in the LEO 138559 treatment group to keep the blinding (as further detailed in a separate trial product handling manual and the blinding plan). The additional injections will include saline solution. During the treatment period, the subject will be asked to continue applying the emollient twice daily (or more frequently, if needed). The subject will be asked to visit the clinic for assessments and procedures for 9 visits (until week 16) as specified in Panel 2. Final dosing will be administered at week 14, regardless of AD improvement.

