#### Safety follow-up period (week 17 to week 32)

In the safety follow-up period, the subject will not receive any treatment with LEO 138559 or comparator injections. The safety of the subject will further be assessed at 3 safety follow-up phone calls (weeks 20, 24, and 28) and at a final safety follow-up visit at week 32. Topical treatment for AD will be permissible during the safety follow-up period. At the end of trial visit the diary will be collected and assessments will be conducted as specified in Panel 2.

Subjects who require treatment with other biologics will prematurely discontinue the trial.

Subjects who discontinue the trial early should be requested to return for an early termination / end of trial visit (see also Section 10.3) at the time of the decision to withdraw from the study.

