#### 14.3.9.1 Adverse events

AEs will be coded during the course of the trial according to Medical Dictionary for Regulatory Activities (MedDRA). AEs will be presented by preferred term and primary system organ class (SOC).

Treatment-emergent AEs will be summarised; however, all AEs recorded during the course of the trial will be included in subject data listings. The tabulations described in the following will only include the treatment-emergent AEs. In each of the tabulations, AEs are defined by MedDRA preferred terms within primary SOC.

AEs will be summarised in terms of the number of subjects with at least 1 event, the percentage of subjects with at least 1 event, the number of events, and the event rate per 100 patient years of observation time.

Related AEs are defined as AEs for which the investigator has not described the causal relationship to IMP as 'not related'.

An overall summary of the number of events and the number (percentage) of subjects with any treatment-emergent AEs, deaths, SAEs, permanent discontinuations from IMP, and/or withdrawals from the trial due to AEs, treatment-related AEs, mild and moderate AEs, and severe AEs will be presented.

Tabulations by SOC and preferred term will be presented for all AEs, SAEs, related AEs, and AEs leading to withdrawal from trial and/or permanent discontinuation of IMP. In addition, all AEs will be presented by severity and causal relationship to IMP, respectively.

The number of AEs and number of subjects with each type of AEs will be tabulated by treatment group from baseline to week 16, from baseline to week 32, and from week 17 to week 32.

AEs leading to withdrawal from trial and/or permanent discontinuation of IMP will be tabulated and listed. The detailed listing will provide an overview of the individual cases and include the age and sex of the subject, treatment received at the time of AE onset, the AE preferred and reported terms, causality and severity of the AE, the action taken with the IMP, AE outcome, start and stop date of AE, duration of AE, and number of days since first and last IMP administration. No narratives will be given.

SAEs will be evaluated separately, and a narrative will be given.

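### The 18-week treatment-emergent limit falls on the nominal day of the final safety visit, so AEs starting at or near that visit enter or leave the week-32 AE tables according to visit timing

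*Combined protocol and SAP*

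**What the plan says.** Section 14.3.6 counts an event as treatment-emergent if it starts, or worsens in severity, after the first dose. It then sets an end point: "An event will not be considered treatment-emergent if starting 18 weeks after the last dose of IMP". It does not say on which side of the limit day 126 falls.

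Section 14.3.9.1 restricts the AE tables to these events ("The tabulations described in the following will only include the treatment-emergent AEs") and plans them for three periods: "from baseline to week 16, from baseline to week 32, and from week 17 to week 32". The same section keeps all recorded AEs in subject listings and gives SAEs a separate evaluation with a narrative.

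The calendar comes from Section 7.1 and Panel 2:
- Treatment period (Section 7.1): "Final dosing will be administered at week 14, regardless of AD improvement".
- Follow-up (Section 7.1): safety is assessed at three "phone calls (weeks 20, 24, and 28) and at a final safety follow-up visit at week 32".
- Panel 2 lists the nominal days of those contacts as "141, 169, 197 225", the last being visit 16. It puts visit 11 (week 14) at day 99 and allows ±3 days at both visits.

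Under Section 13.2, AEs are collected "until subject's completion of the clinical trial", which means through the week 32 visit. Under Section 13.3 an AE is dated by its start.

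**The concern.** The tables for baseline to week 32 and for weeks 17 to 32 read as if they cover the whole collection period. The definition does not guarantee that.

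Visit 16 is the only scheduled follow-up visit at which laboratory tests, ECG, vital signs and physical examination are done. The eCRF reporting rules in Sections 11.4.1, 11.4.2, 11.4.4 and 11.4.5.2 turn new clinically significant findings there into AEs. No rule says how to date an abnormality first seen at a visit. A silent one may well be dated to the visit itself, which is where the limit falls.

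Other tables make up for this only in part. The shift tables for physical findings and ECG (14.3.9.2, 14.3.9.3) stop at week 16, and the laboratory shift table (14.3.9.4) stops at end of treatment. A non-serious examination finding that starts at visit 16 could therefore appear in listings and in no table.

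Safety is the secondary objective. With about 8 subjects on LEO 138559 and 4 on the comparator, one or two events visibly change a descriptive table.

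**Working it through.** **Inputs.** Last dose: week 14, day 99 (Section 7.1, Panel 2). Visit 16: week 32, day 225 (Panel 2). Windows: ±3 days at visits 10, 11 and 16 (Panel 2). Limit: 18 weeks after last dose (14.3.6).

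**1. Nominal calendar.** The study day of week w is 1 + 7w.
- Last dose: 1 + 7 × 14 = 99.
- Visit 16: 1 + 7 × 32 = 225, which reproduces Panel 2.
- Limit: 99 + 7 × 18 = 99 + 126 = 225.

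The limit and the visit fall on the same day.

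**2. Range of the gap.** The last dose can be on days 96 to 102 and visit 16 on days 222 to 228. The gap runs from 222 − 102 = 120 to 228 − 96 = 132 days.

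**3. Share of completers at or past the limit.** The documents do not say how visits spread within their windows, so this step is an assumption. Take the two offsets as independent and uniform over 7 days each, giving 49 pairs. In 7 pairs the gap is exactly 126 days; the other 42 split evenly.
- Gap ≥ 126: (7 + 21)/49 = 28/49 = 57.1%.
- Gap > 126: 21/49 = 42.9%.

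If all of 12 subjects complete, that is about 6.9 or 5.1 subjects.

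**4. Sensitivity to clustering on the nominal day.** Let p be the probability that a visit is on its nominal day, with the rest spread evenly over the other 6 days. The probability of a gap of exactly 126 days is t = p² + (1 − p)²/6. The two shares are then (1 + t)/2 and (1 − t)/2.

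| p | gap ≥ 126 | gap > 126 |
|---|---|---|
| 1/7 (uniform) | 57.1% | 42.9% |
| 0.5 | 64.6% | 35.4% |
| 0.9 | 90.6% | 9.4% |
| 1 | 100% | 0% |

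The better sites keep to schedule, the more the unstated inequality alone decides the result.

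**5. Missed week 14 dose.** Take a subject who misses that dose without permanently discontinuing. The last dose is at week 12, day 85, and the limit is nominally 85 + 126 = day 211 (week 30). That is 225 − 211 = 14 days before visit 16. Even at the window edges the gap is at least 222 − 88 = 134 days. AEs starting in about the last two weeks of collection are excluded under either inequality.

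**6. What is not affected.**
- Permanent discontinuers: Section 10.3 sets their final visit 16 weeks after last dose. That is 112 days, 14 days inside the limit.
- Secondary endpoint (to week 16): with a last dose as early as day 1, the limit is 1 + 126 = day 127. This is later than day 113, or day 116 with the window.

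**The case against.** The rule acts on when an event starts, not on when it is found. An event reported at visit 16 with an earlier onset stays in the tables, so it would be wrong to infer that everything first detected at that visit is lost. This stands, and it limits the point to events whose start date is at or past the limit.

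Much of the data survives elsewhere. Listings keep every AE, SAEs have narratives, and laboratory, ECG and vital-sign changes are summarised by visit without a treatment-emergent filter (14.3.9.2 to 14.3.9.4). Clinically significant physical and ECG findings are listed. In a descriptive trial of about 12 subjects, listings can be read directly. This stands too. The by-visit summaries, however, are means, medians and ranges, and do not replace an AE count.

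Visit 16 is not the only possible occasion for finding an abnormality, because Section 7.1 and Panel 2 allow unscheduled visits with the same assessments. It is the only scheduled one.

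An 18-week limit is pharmacologically reasonable. With the half-life of 21 to 25 days in Section 5.2, 126 days is 5.0 to 6.0 half-lives, leaving 0.5^(126/25) = 3.0% to 0.5^(126/21) = 1.6% of the drug. That supports a limit of roughly this length. It does not support a limit that cuts through the last assessment visit while the table headings run to week 32.

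Finally, Section 14.3.12 defers to a statistical analysis plan finalised before unblinding, which could settle the boundary. The document under review contains no such text, and 14.3.6 is the rule as it stands.

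**Conclusion.** The point holds for AEs that start at or near visit 16. The limit coincides exactly with that visit's nominal day, day 126 is not assigned to either side, and a few days of scheduling decide whether such an event is counted in the two tables that reach week 32. A missed week 14 dose without permanent discontinuation moves the limit about two weeks before the end of collection.

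The share of completers whose visit 16 falls at or past the limit is 43% to 57% under independent, uniform visit timing. It is 0% or 100% if all visits are on the nominal day. A reader might infer that about half of subjects lose findings. The documents do not support that: the figure rests on the assumed spread, and it describes visit timing, not the number of events lost, which may be none or very few. A reader might also infer that the off-treatment AE tables are wrong. They are better described as potentially incomplete and dependent on visit timing. The change should be made, but it is a modest one.

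**What to change.** In 14.3.6, replace the 18-week sentence with a rule along these lines: *for the AE tables, events starting (or worsening) after the first dose, up to and including the end-of-trial visit (visit 16, with its window), are treatment-emergent.* Show days since last dose for any event starting more than 18 weeks after it, so that late events can be recognised. State how an abnormality first seen at a visit is dated. The secondary endpoint keeps its own limit at week 16.

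This changes an analysis definition only. It needs no new data and no change to treatment or visits. The cost is that a few late background events may enter the tables.

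Separately, Section 12.1 describes safety follow-up as 16 weeks after last dose, whereas the schedule gives 18 weeks (week 14 to week 32). These passages must be reconciled.
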